Commercially available DBS leads in the US consist of a linear array of ring-shaped electrodes. We are studying segmented leads developed by Boston Scientific to steer current and better optimize DBS efficacy and tolerability in individuals. Evidence from recent studies in Europe by Timmermann et al and Volkmann et al suggest that this current steering approach is feasible for these purposes, however it is possible that the activation of individual segments alone will not provide therapeutic benefit or that they will not improve the thresholds for potential side effects from DBS in individual patients. If this were the case, we can still activate all three segments simultaneously so that the individual segments act together as a traditional ring electrode.

15. Participants (Screening and Selection)

a. How many participants are to be enrolled at UAB? 40

If multi-center study, total number at all centers:

Not applicable, this is a single center study

b. Describe the characteristics of anticipated or planned participants.

Sex: Both

Race/Ethnicity: All

Age: 18 - 70

Health status:

Patients who undergo deep brain stimulation (DBS) as part of routine care for Parkinson's Disease

Note. If data from prior studies indicate differences between the genders or among racial/ethnic groups in the proposed research or if there are no data to support or to negate such differences, Phase 3 clinical trials will be required to include sufficient and appropriate entry of gender and racial/ethnic subgroups so that trends detected in the affected subgroups can be analyzed. If ethnic, racial, and gender estimates are not included in the protocol, a clear rationale must be provided for exclusion of this information. If prior evidence indicates that the results will not show gender or racial differences, researchers are not required to use gender or race/ethnicity as selection criteria for study participants. They are, however, encouraged to include these groups. See Section II. Policy of the NIH POLICY AND GUIDELINES ON THE INCLUSION OF WOMEN AND MINORITIES AS SUBJECTS IN CLINICAL RESEARCH – Amended, October, 2001) for further details.

c. From what population(s) will the participants be derived?

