Intraoperative ERP assay: DBS surgery occurring electively as part of routine care. We only consent patients after the patient has been approved for surgery for routine care. Our research approach in the OR uses a unique electrophysiological assay to measure cortical activation by DBS with high bandwidth simultaneous EEG, ECOG (over pre-motor, primary motor, and primary sensory cortices), and 8 contralateral surface EMG electrodes. We measure cortical activation by DBS in a dose-dependent manner, elicited from the entire spatial extent of the implanted lead. EEG, ECOG, and EMG are validated modalities that have been in worldwide clinical use for decades. As such, putative biomarkers from this study have the potential for broad, immediate application. Our unique electrophysiology approach allows (1) remarkable stimulus artifact removal; (2) accurate detection of small differences in ERP latency; (3) explicit control of the timing, waveform, and pattern of the stimuli, (4) fully automated stimulus protocol delivery, and (5) markedly faster post-processing. This allows us to evaluate hypotheses that were untestable in prior DBS studies. We use our externalized pulse generator to randomize stimulus amplitude (0 to 5 mA in 1 mA increments), location (anode/cathode pair), and interstimulus interval (mean 100±20 ms) on a pulse by pulse basis. We will elicit ERPs only from adjacent electrode pairs, yielding 25 stimulation conditions. Based on extensive prior work, 100 stimulation events (50 in each anode/cathode pair) is more than sufficient to generate an ERP in the vast majority of participants. The total duration of the assay is 24.0 minutes.

Neuroimaging Battery: All imaging studies including MRI and CT occur as part of routine care. Data from the imaging studies will be used for research purposes. Imaging will occur (1) pre-operatively for screening and diagnostic purposes, (2) to inform routine stereotaxy on the day of surgery, (3) to localize ECOG, EEG, and DBS electrodes during surgery, and (4) to confirm lead placement and screen for potential adverse events after surgery.

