Success Criteria:	All subjects follow research protocol as summarized in Error! Reference source not found. and Error! Reference source not found. Follow-up at 1 year post-crossover completion with ≥80% of the participants.
Rationale:	Overall randomization and study design has been approved by NIH staff. As this is a deviation from what was originally in the proposal, this new study design should be followed. All further deviations should be negotiated and approved by NIH prior to changes being made.
Milestone 3.6:	Review IRB and IDE paperwork to ensure both are up to date and allow for a sufficient scope and number of subjects for successful completion of work proposed in the upcoming year.
Success Criteria:	Confirm paperwork is up to date and NINDS staff has the most recent version.
Rationale:	Maintaining IRB and IDE approval is a requirement for a clinical study.

Year 4

Milestone 4.1:	Maintain active membership status in NIH-coordinated data sharing consortium.
Success Criteria:	Actively participate in the data sharing consortium, and adopt best practices/efforts to comply with the recommendations of the data sharing consortium, throughout all years and/or stages of the award.
Rationale:	Participation and maintaining an active membership status in the consortium is a requirement of the RFA.
Milestone 4.2:	Complete the pre-operative assessment battery and implant the Boston Scientific Vercise DBS system with the directional lead in at least 3 additional participants in Y4, for a total of at least 30 enrolled and implanted participants.
Success Criteria:	Successfully implant the Vercise DBS system with directional lead, extension cable, and pulse generator in 3 participants using standard STN stereotaxy. Successful implant is defined as placement of the entire DBS system without surgical adverse events (such as stroke, infection, seizure) or any other adverse event that prevents postoperative device activation, adjustment,

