Noninvasive Biomarkers to Advance Emerging DBS Electrode Technologies in Parkinson's Disease
(SUNDIAL, SUBthalamic Nucleus DIrectionAL vs Circular Stimulation Study)

NCT03353688

11/30/2023

Statistical Analyses. Each patient participates in all sub-Aims, therefore overall sample size is determined by the sub-Aim requiring the largest sample.

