SA1. To test the hypothesis that specific contacts on a novel segmented DBS lead in the STN region activate functionally distinct populations of cortical axons within individual PD patients. SA1.1 will measure within-participant contrasts in therapeutic window and UPDRS part 3 change versus pre-op baseline across the different segments on the directional DBS lead with two-way repeated measures mixed models using Proc Mixed in SAS, with conventional versus current steering DBS contacts as factors and therapeutic window and change in UPDRS part 3 as data. The primary outcome measure for SA1.2 will compare whether intraoperative ERPs predict within-participant changes in the clinical outcomes from SA1.1. We will contrast the ERPs within and across stimulation sites with two-way repeated measures mixed models using Proc Mixed in SAS, with stimulus amplitude, location, and recording modality (EEG or ECOG) as factors and P1/N1 latency and HFO integrated area as data. Using linear contrasts from the regressions, we will directly compare whether EEG and ECOG measures of DBS amplitude thresholds (1) that change P1/N1 latency and (2) elicit the large amplitude HFOs better predict the size of the therapeutic window for a given DBS electrode contact. Secondary outcomes will correlate these amplitude thresholds with changes in the UPDRS part 3 score, UPDRS subscores, and other elements of the Motor battery measured in SA1.1. To control for potential subclinical corticospinal tract activation, we will report the latency and magnitude of EMG response(s) in the contralateral arm and leg muscles using residual analyses, when and if these responses are present. Sample size for SA1. Our preliminary findings show robust within- and between-subject changes in ERP latency that predict postoperative motor side effects. For the first primary outcome, a sample size of 18 will have 80% power to detect a difference between a null hypothesis regression slope of 0 and an alternative regression slope of 0.3 or higher standardized units, assuming that the standard deviation of the predictor variable, DBS amplitude threshold, is 2.370 mA (the standard deviation of the stimulus intensities) and the standard deviation of the normalized residuals ($sd=1$) of the therapeutic window using a t-test with a 0.05 two-sided significance level. Thus, we will be overpowered for SA1, because a large sample of 30 is dictated by SA2.3. As an additional secondary analysis, we will compare the predictive power of EEG versus ECOG, we will first regress the primary outcomes on EEG and then determine how much of the residual variance is explained by ECOG. If EEG explains 50% of the variance in the primary outcome, then we will have 80% power to detect an increase in the R-square of 8.6%. If the additive R-square of EEG is 25%, we will have 80% power to detect an increase of 12.9%. If we cannot demonstrate superiority of ECOG, we would default to the less invasive modality. We will look at the assumptions of the model by examining the residual plots in the regression models for both modalities.

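### SA1's 80% power with 18 patients uses a predictor SD of 2.370 mA that does not follow from its named source, and the R-square increments for SA1 fit 40 patients rather than the 30 cited

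*SAP*

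**What the plan says.** The SAP opens with the rule that "Each patient participates in all sub-Aims, therefore overall sample size is determined by the sub-Aim requiring the largest sample". For SA1, under Sample size for SA1, it claims 80% power with 18 patients to detect a regression slope of 0.3 standardized units against zero. The outcome is therapeutic window with normalized residuals (SD 1), tested by a two-sided t-test at 0.05, "assuming that the standard deviation of the predictor variable, DBS amplitude threshold, is 2.370 mA (the standard deviation of the stimulus intensities"). It then concludes: "Thus, we will be overpowered for SA1, because a large sample of 30 is dictated by SA2.3".

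In the same paragraph, for the secondary comparison of EEG with ECoG, the SAP says that if EEG explains 50% of the variance, "then we will have 80% power to detect an increase in the R-square of 8.6"%. If EEG explains 25%, the increment is 12.9%. No n is given for either figure.

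Protocol item 16a (Intraoperative ERP assay) gives the stimulus levels: the external generator will "randomize stimulus amplitude (0 to 5 mA in 1 mA increments"). On numbers of patients, protocol item 15a reads "How many participants are to be enrolled at UAB? 40", and Milestone 4.2 sets a minimum, "for a total of at least 30 enrolled and implanted participants".

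**The concern.** The SAP names the source of its predictor SD. The one set of stimulus intensities in the documents that matches the description has a smaller SD. In a slope test the noncentrality is proportional to the predictor SD, so an SD that is too large makes the required n too small.

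This is the SAP's only power statement for the first primary outcome of SA1, and the conclusion that SA1 has power to spare rests on it. As written, the reserve is 12 patients (30 − 18). If the stated intensities are used, the reserve on the same method largely disappears at 30.

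The second problem is which n the SA1 statements refer to. One sentence uses 30. The R-square statements appear to use another number.

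**Working it through.** **Inputs.** From the SAP: slope 0.3, residual SD 1, predictor SD 2.370 mA, two-sided alpha 0.05, n = 18 and n = 30. From the protocol: levels 0, 1, 2, 3, 4, 5 mA and planned enrolment of 40.

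**Method.** Simple linear regression, one observation per patient. Noncentrality = slope × SD × √n / residual SD, with n − 2 degrees of freedom, and power from the noncentral t.

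**Step 1: reproduce the SAP.** At n = 18 the noncentrality is 0.3 × 2.370 × √18 = 3.017. With 16 df and critical t 2.120, power is 80.8%. At n = 17 it is 78.2%. So 18 is the smallest n that reaches 80%, and the arithmetic is sound given its inputs. It reproduces only if the slope is read as 0.3 residual SDs per mA. Read as 0.3 per SD of the predictor, power at 18 would be about 22%. The SAP does not state the unit or say that there is one observation per patient; both are inferred from the match.

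**Step 2: SD of the stated intensities.** The mean of 0 to 5 is 2.5 and the sum of squared deviations is 17.5. With divisor 6, SD = √2.917 = 1.708; with divisor 5, SD = √3.5 = 1.871. Equal use of the levels is assumed. Without 0 mA, which is no stimulus, the sum of squares is 10 and SD = √2 = 1.414 or √2.5 = 1.581.

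**Step 3: same method, other SDs.**

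| Predictor SD (mA) | Power at 18 | Power at 30 | Power at 40 | n for 80% |
|---|---|---|---|---|
| 2.370 (SAP) | 81% | 96% | 99% | 18 |
| 1.871 (0–5 mA) | 61% | 84% | 93% | 27 |
| 1.708 (0–5 mA) | 53% | 77% | 88% | 32 |
| 1.581 (1–5 mA) | 47% | 71% | 83% | 37 |
| 1.414 (1–5 mA) | 40% | 61% | 74% | 46 |

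On the 0–5 mA set, the reserve at n = 30 is between 30 − 27 = +3 and 30 − 32 = −2 patients. At n = 40 it is between +8 and +13.

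**Step 4: R-square increments.** Effect size f² = increment / (1 − R² of EEG − increment).
- 0.086 / (1 − 0.50 − 0.086) = 0.2077
- 0.129 / (1 − 0.25 − 0.129) = 0.2077

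Both figures are therefore the same effect size. Power from the noncentral F with 1 and n − 3 df and noncentrality n × f² is 80.2% at n = 40 and 67.3% at n = 30. At n = 30 the increments detectable with 80% power are about 11.0% and 16.5%.

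**The case against.** The strongest objection concerns the planned analysis. It is not a one-observation-per-patient regression. The SAP specifies mixed models and asks which measures "better predict the size of the therapeutic window for a given DBS electrode contact", so several contacts per patient contribute. If thresholds differ between contacts, as SA1's hypothesis supposes, power can be much higher.

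A check under assumed values: 30 patients, 8 contacts, SD 1.708, slope 0.3, within-patient outcome correlation 0.5, and only 10% of threshold variance within patients.
- Within-patient information: 30 × 7 × 2.917 × 0.1 / 0.5 = 122.5
- Between-patient information: 30 × 2.917 × (0.9 + 0.1/8) / (0.5 + 0.5/8) = 141.9
- Noncentrality: 0.3 × √264.4 = 4.88, so power is above 99%

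This objection stands. A reader might infer from the table that SA1 is underpowered, or that 18 patients really give 53–61%. The documents do not support either reading. The table tests the SAP's simplified calculation, not the planned model, for which the SAP gives no power.

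A second objection is that 2.370 may have a source we cannot see. The sample-size paragraph opens by referring to preliminary findings, and protocol item 23 says that the grant application containing them was attached. The predictor is a threshold, whose SD need not equal that of the delivered levels; values confined to 0–5 mA can have an SD as high as 2.5. So 2.370 is not impossible. What remains is that the SAP itself describes 2.370 as the SD of the intensities, and the stated intensities do not give it.

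Third, 30 and 40 need not conflict. The ERPs are recorded at surgery, before the crossover, so SA1 could use 40 and SA2.3 could use 30. The SAP does not say this, and its statement about excess power refers to 30.

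**Conclusion.** The 80% power with 18 patients follows from an SD of 2.370 mA, but that SD does not follow from the source given for it. On the only stated intensities, equally used, the same method needs 27 to 32 patients, or 37 to 46 if 0 mA is left out. Power on 0–5 mA is 77–84% at 30 and 88–93% at 40. These values show how far the claim depends on the SD; they do not replace it.

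The R-square increments match 40 patients and not the 30 cited in the same paragraph. That n is back-calculated, and the increments belong to a secondary analysis.

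It would go too far to conclude that SA1 is underpowered or that the trial needs more patients. SA2.3 sets the sample size, three of the four power values for 0–5 mA at 30 or 40 exceed 80%, and the per-contact mixed model may have far more power. The supported conclusion is narrower: the stated n, the stated reserve and the claim of excess power are not backed by the inputs that the documents give.

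**What to change.** 1. Reconcile the SAP's SA1 sample-size paragraph with the stimulus levels in protocol item 16a. Either cite the data behind 2.370 mA as an SD of amplitude thresholds, or replace it with a sourced SD and restate the n for 80% power and the power at the n used for SA1.
2. State that the slope of 0.3 is in residual SDs of therapeutic window per mA, and that the calculation assumes one observation per patient.
3. State once whether SA1 uses 30 or 40 patients, and make the R-square increments match: 8.6% and 12.9% at 40, or about 11.0% and 16.5% at 30.
4. Qualify the statement that SA1 has more power than it needs. Alternatively, support it with a power calculation for the planned mixed model that gives the number of contacts and the within-patient variation of both threshold and outcome.

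The cost is SAP wording and a short recalculation, or a small simulation if the mixed model is used. Sample size, endpoint and decision rule do not change.

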selected based cortical ERP physiology, using both therapeutic window and change in UPDRS part 3 as data nested within person. Secondary analyses will contrast the efficacy of these DBS adjustment strategies based upon changes in other elements of the Motor battery. In SA 2.3, we use the randomized, doubleblind crossover trial to compare changes in UPDRS and other measures of quality of life and motor, cognitive, behavioral, and speech function across the DBS programming strategies identified in SA 2.1. The primary statistical analysis will use Proc Mixed in SAS with active contact groupings including (1) conventional DBS, (2) multiple active contacts selected based on behavior, and (3) multiple active contacts based on ERPs as factor and patient preference and changes in PDQ-39 and UPDRS part 3 as data. Sample size for SA2. We will obtain multiple repeated measures within participants and can readily detect changes in patient preference, PDQ-39, UPDRS part 3, and other motor and non-motor variables of interest. Patient reported evidence for the hypothesis of superiority of current steering will be shown by determining that 20 or more of the 30 participants favor either current steering approach over conventional DBS using a binomial distribution based on patient preference (vote), PDQ-39, and UPDRS part 3. This would achieve a p value of < 0.049 . We will declare current steering DBS to be clinically superior to conventional therapy based on patient preference if 20 or more patients meet this criterion. We will measure the frequency by which current steering provides better outcomes versus conventional DBS, which could still be highly relevant and significant clinically (even if preferred by <20 participants). Secondary measures will quantify within-participant changes in upper limb dexterity, gait speed test, posture and balance, cognitive/behavioral measures, speech, and motor diaries. Additionally, we will contrast the probability that active contacts are shared among the programming strategies (conventional DBS, current steering guided by behavior, and current steering guided by cortical physiology). The extent to which contacts and stimulation parameters are shared among these approaches could be informative and provide a useful internal validation of the current steering approach.

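### The 80% power stated for ECoG's added R-square (8.6% and 12.9%) fits 40 patients; at the 30 the SAP applies to SA1, power is about 67%

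*SAP*

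**What the plan says.** The SAP opens its statistical section with one rule for sample size: "Each patient participates in all sub-Aims, therefore overall sample size is determined by the sub-Aim requiring the largest sample". In the SA1 sample-size paragraph it first justifies n = 18 for the slope test, "using a t-test with a 0.05 two-sided significance level". It then concludes that "we will be overpowered for SA1, because a large sample of 30 is dictated by SA2.3".

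The next sentence introduces the comparison at issue: "As an additional secondary analysis, we will compare the predictive power of EEG versus ECOG". The method is hierarchical: EEG is entered first, then ECoG is assessed on what remains. Two power statements follow:

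- EEG R-square 50%: "then we will have 80% power to detect an increase in the R-square of 8.6" percent.
- EEG R-square 25%: "we will have 80% power to detect an increase of 12.9" percent.

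Neither statement gives an N, an alpha, a unit of analysis or a number of ECoG predictors. The decision attached to the result is: "If we cannot demonstrate superiority of ECOG, we would default to the less invasive modality".

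The SA2 paragraph also works with 30, in its rule of "20 or more of the 30 participants favor either current steering approach over conventional DBS". The number 40 does not appear in the SAP. It is the enrolment number in protocol section 15 (items a and c). The protocol's milestones for Year 4 set 30 as the goal for implantation and randomization.

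**The concern.** Anyone reading the SA1 paragraph in order will take the two 80% statements as holding at 30, the only sample the SAP gives for SA1 beyond the 18 of the slope test. They do not appear to hold there. The remark that SA1 is overpowered is fair for the slope test (about 96% power at n = 30 by the same calculation that gives n = 18), but it does not carry over to the R-square comparison.

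The stake is how a null result is read. If ECoG does not add significantly to EEG, the SAP falls back on the less invasive modality. A reader who believes the power was 80% will think a true increment of 8.6% or 12.9% would be missed one time in five. At 67% power it would be missed about one time in three.

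**Working it through.** **Inputs.** From the SAP's SA1 sample-size text: base R-square 0.50 with increment 0.086; base R-square 0.25 with increment 0.129; power 80%; n = 30; two-sided 0.05. The alpha is stated there for the slope test and carried over here. Assumed, because not stated: the patient is the unit, with one EEG term (p₀ = 1) and one added ECoG term (k = 1).

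**Step 1. Check the convention on the SAP's own n = 18.** Slope 0.3 × predictor SD 2.370 / residual SD 1 = 0.711. Noncentral t, df = n − 2, noncentrality 0.711 × √n:

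- n = 17: noncentrality 2.93, power 78.2%
- n = 18: noncentrality 3.02, power 80.8%

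So 18 is the smallest n reaching 80%. The patient-level, two-sided 0.05 convention reproduces the SAP's figure.

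**Step 2. Effect size of the two increments.** f² = ΔR² / (1 − R²_full).

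- EEG 50%: 0.086 / (1 − 0.586) = 0.086 / 0.414 = 0.2077
- EEG 25%: 0.129 / (1 − 0.379) = 0.129 / 0.621 = 0.2077

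They are the same effect, so both figures are consistent with one calculation at one N.

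**Step 3. Which N gives the printed figures?** Noncentral F with df₁ = k = 1, df₂ = n − p₀ − k − 1 = n − 3, and λ = n × f². To find the detectable increment, solve for the f² that gives 80% power; then ΔR² = (1 − R²_EEG) × f² / (1 + f²).

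| n | Power at f² = 0.2077 | Detectable at 80%, EEG 50% | Detectable at 80%, EEG 25% |
|---|---|---|---|
| 30 | 0.6725 | 10.98% | 16.48% |
| 39 | 0.7909 | 8.76% | 13.15% |
| 40 | 0.8015 | 8.57% | 12.86% |
| 41 | 0.8116 | 8.39% | 12.58% |
| SAP | 0.80 | 8.6% | 12.9% |

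Under this model only n = 40 rounds to both printed figures. As a worked line for n = 30, 80% power needs f² = 0.2816, so 0.50 × 0.2816 / 1.2816 = 0.110 and 0.75 × 0.2816 / 1.2816 = 0.165.

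**Step 4. Can another patient-level reading rescue n = 30?**

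- Two ECoG terms, since the SAP names two ERP thresholds (P1/N1 latency and HFO): power about 55%; detectable increments about 13.3% and 20%.
- λ = (n − 1) × f²: power 66% at n = 30; 80% is first reached at n = 41.
- Predictors treated as random (simulation): about 63% at n = 30. Fisher z for the partial correlation: 61%.
- One-sided 0.05: power 78.5%, but the detectable increments are 8.9% and 13.4%, not the printed pair. An R-square increase also has no direction, and the SAP states two-sided.

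None of these returns both printed figures at n = 30.

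**Sensitivity only.** If fewer than 30 patients had usable paired EEG and ECoG data (an assumption, not a forecast), one-term power would be 57% at n = 24 and 53% at n = 22.

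**The case against.** The strongest counter-argument concerns the unit. SA1 predicts the therapeutic window of individual contacts, uses repeated-measures mixed models, and the lead has 8 contacts. With several observations per patient, the effective sample exceeds 30. As an illustration with assumed intraclass correlations, 30 × 8 = 240 observations divided by a design effect of 1 + 7 × ICC give an effective n of about 53 at ICC 0.5 (power about 90%), 41 at 0.7 (about 81%) and 33 at 0.9 (about 72%). So 67% is not established as the power of the analysis that will be run. That stands as a limit on the figure. It does not support the printed figures, because the SAP gives no contact-level N or correlation from which they could have been derived.

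Second, reproducing n = 18 validates the convention for a different test. And n = 40 is singled out only under the one-predictor model: with other predictor counts or another noncentrality convention, both printed figures can also arise at n = 41, 50 or 57. This weakens the inference that 40 was used. The mismatch with 30 remains, since every match lies well above 30.

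Third, 40 is a real number in this trial. SA1 data come from surgery and the monopolar survey, before the crossover, so SA1 could include more patients than the 30 randomized. If that was intended, the figures are right and only the label is missing. But the SAP itself applies 30 to SA1, so the two must still be reconciled.

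Finally, the comparison is secondary, sets no sample size, and low power errs towards the less invasive option. This limits the consequence but does not make the stated power correct.

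**Conclusion.** The concern holds. The stated 80% power for added ECoG R-square of 8.6% and 12.9% is not what the sample of 30 delivers under the convention that reproduces the SAP's other SA1 figure. On that convention (one ECoG term, patient as unit, two-sided 0.05), power at 30 is about 67%, a shortfall of some 13 percentage points. The increments detectable with 80% power are 11.0% and 16.5%, about 28% larger than stated (10.98 / 8.6 and 16.48 / 12.9 both give 1.28). The printed figures match n = 40 to the decimal.

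The mismatch with 30 is firm across the patient-level variants checked. The exact size depends on the unit and predictor count, which the SAP leaves open. The matter should be corrected, but it touches a secondary analysis only.

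**What to change.** In the SA1 sample-size paragraph, state the N, unit of analysis, number of EEG and ECoG predictors, and alpha for the R-square calculation, and recompute from them.

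- If the model is patient-level with one ECoG predictor and n = 30, report either 80% power for increments of 11.0% and 16.5%, or about 67% power for 8.6% and 12.9%.
- If 40 is the intended N, say so and reconcile it with the 30 applied to SA1.
- If contacts are the unit, give the number per patient and the assumed within-patient correlation, and derive the figures from those.

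Any power for fewer evaluable patients should be shown only as a sensitivity range. The cost is a few sentences in the SAP and, at n = 30 under the patient-level model, less favourable detectable increments. Enrolment, the primary test and patient procedures do not change.

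### The SAP does not define ECoG superiority, and the analysis next to the modality decision (R-square gain of ECoG after EEG) tests added information, not better prediction

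*SAP*

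**What the plan says.** The relevant text is in the SAP, Statistical Analyses, SA1, in the sample-size paragraph. An additional secondary analysis is introduced with the aim "we will compare the predictive power of EEG versus ECOG". The method is sequential: "we will first regress the primary outcomes on EEG and then determine how much of the residual variance is explained by ECOG". Two power statements follow. If EEG explains half of the variance, "then we will have 80% power to detect an increase in the R-square of 8.6" percent. The other reads "If the additive R-square of EEG is 25%, we will have 80% power to detect an increase of 12.9" percent. The next sentence is the decision: "If we cannot demonstrate superiority of ECOG, we would default to the less invasive modality".

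No criterion for superiority is given, and no model is described in which EEG is added after ECoG. Earlier in the same section, under SA1.2, the SAP plans linear contrasts that compare directly whether EEG or ECoG amplitude thresholds better predict the therapeutic window of a contact. There are two such thresholds, one for a change in P1/N1 latency and one for the high-frequency oscillation. The SAP does not connect those contrasts to the modality decision.

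**The concern.** The stated aim is a comparison of predictive strength, but the analysis described and powered answers a different question. Testing ECoG after EEG asks whether ECoG holds anything that EEG lacks. Two imperfectly correlated measures of equal quality each add to the other, so a significant gain is expected without either being better. Reversing the order would appear to favour EEG just as often, but the reverse order is not planned.

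At stake is a conclusion about whether a subdural strip, whose incremental risk the protocol discusses in its Risks section, predicts better than a scalp recording. The default to the less invasive modality shows that the authors want real evidence before preferring ECoG. A significant gain is weaker evidence than that. The problem also grows as the biomarker gets better, because the true gain under equality is proportional to R².

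**Working it through.** **Inputs.** From the SAP: EEG R-square of 25% or 50%; detectable gains of 12.9 and 8.6 percentage points at 80% power; sample size, "a large sample of 30 is dictated by SA2.3". The significance level is stated for the SA1 slope test ("using a t-test with a 0.05 two-sided significance level") and is assumed here for the gain as well. The EEG–ECoG correlation r is in neither document, so it is an assumption, shown as a range.

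**1. The SAP's own power figure.** For a partial F test with 1 and N−3 degrees of freedom, f² = gain/(1 − R² − gain) and λ = N·f².
- EEG 50%: 0.086/(1 − 0.50 − 0.086) = 0.086/0.414 = 0.208.
- EEG 25%: 0.129/(1 − 0.25 − 0.129) = 0.129/0.621 = 0.208.
- N=30: λ = 6.23, power 67% in both scenarios. The gains detectable with 80% power would be 11.0 and 16.5 points.
- N=40: λ = 8.31, power 80%. This matches the SAP, and 40 is the protocol's enrolment figure ("How many participants are to be enrolled at UAB? 40").

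The powered test is therefore the gain of ECoG after EEG. Which N was intended is a separate question and does not affect this point.

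**2. True gain when neither modality is better.** Let both correlate c with the outcome, with c² = R², and r with each other. The joint R-square is (c² + c² − 2c²r)/(1 − r²) = 2c²/(1 + r). Subtracting c² leaves

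gain = R²(1 − r)/(1 + r).

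At R²=25% and r=0.5 this is 0.25 × 0.5/1.5 = 8.3 points. Solving for r with k = gain/R² gives r = (1 − k)/(1 + k).
- 12.9 points at 25%: k = 0.516, r = 0.484/1.516 = 0.32.
- 8.6 points at 50%: k = 0.172, r = 0.828/1.172 = 0.71.

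The gains that the SAP is powered to find can therefore arise from two equal modalities.

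**3. How often equality would be called ECoG superiority.** Trivariate-normal simulation: n=30, one value per participant, one predictor per modality, gain tested at 0.05.

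| r | True gain, R² 25% | Significant | True gain, R² 50% | Significant |
|---|---|---|---|---|
| 0.3 | 13.5 points | 65% | 26.9 points | >99% |
| 0.5 | 8.3 | 43% | 16.7 | 93% |
| 0.7 | 4.4 | 25% | 8.8 | 64% |
| 0.8 | 2.8 | 17% | 5.6 | 43% |
| 0.9 | 1.3 | 11% | 2.6 | 23% |

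The reverse test, EEG after ECoG, is significant equally often. A Williams test of the two dependent correlations favours ECoG in 2–3% of trials in all these settings. At N=40 and R² 25%, the gain is significant in 78% (r=0.3) and 22% (r=0.8).

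**4. ECoG truly worse.** With EEG at 25% and ECoG at 15%, the gain is still significant in about 33%, 16% and 6% of trials at r=0.3, 0.5 and 0.7.

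**5. Power of a head-to-head test.** Suppose ECoG is better by the SAP's own 12.9 points (25 + 12.9 = 37.9% against 25%). At n=30 the Williams test has power of about 9% at r=0.3, 16% at 0.7, 22% at 0.8 and 39% at 0.9.

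**The case against.** The strongest reply is that the SAP never says the gain is the criterion. The link rests on sentence order, and SA1.2 already contains a direct comparison, placed with the primary outcome, that could decide. This stands in part. A reader might infer that the plan expressly adopts the gain as its superiority test, or that it has no head-to-head comparison; the text supports neither. But if the contrasts are meant to decide, the SAP needs to say so, and its power figures then do not describe the deciding test. Much the same edit is needed on either reading.

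A second reply is that EEG first, with EEG as the default, is a sensible order for asking whether an invasive recording is worth having. That also stands: added value is a legitimate question, and EEG wins whenever the gain is not shown. The fault is in treating the answer as superiority.

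Third, the rates depend on inputs that the documents do not supply. EEG and ECoG are recorded simultaneously to the same pulses (protocol, item 16a), so a high r and the lower rates cannot be ruled out. The SAP also works per contact, with several contacts per participant, whereas the simulation uses one value each. The percentages are illustrative; the algebra in step 2 does not depend on the simulation.

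**Conclusion.** The concern holds in this form: the criterion for ECoG superiority is undefined, and the analysis that most naturally supplies it tests added information. If the gain is used, equal modalities would be called ECoG-superior more often than the 2–3% of a head-to-head test. The illustrative rates are 11–65% for r from 0.9 to 0.3 at EEG R-square 25%, and 23–93% for r from 0.9 to 0.5 at 50%. They assume n=30, two-sided 0.05, one value per participant and the stated r.

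Two stronger inferences are not supported. A reader might take any single range as the plan's error rate at its 25% scenario. It is not, because r is not given; over r from 0 to 0.95 the same calculation runs from about 93% down to 7%. A reader might also infer that a wrong answer would change participants' care. The protocol says that the assay does not alter surgical decisions (item 19a), and nothing ties this secondary comparison to contact selection in the crossover. The consequence is a possibly wrong published conclusion about which modality predicts better. The SAP should be corrected, but this does not threaten the trial's main comparisons.

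**What to change.** Amend SA1 as follows.

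- State that ECoG superiority is decided only by a head-to-head comparison of predictive strength for therapeutic window. Make the direct EEG-versus-ECoG comparison already planned in SA1.2 the deciding one.
- Name one threshold measure (P1/N1 latency or high-frequency oscillation) for that decision.
- Specify the method, for example a paired bootstrap interval for the difference in R-square that resamples whole participants, since each contributes several contacts. Conclude superiority only if the interval lies above zero in ECoG's favour.
- Keep the R-square gain, run it in both orders, and report it as added value.

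The cost is a few lines of text and one further analysis of data already being collected. The downside to disclose is power: about 9–39% at n=30 in the case worked above. The plan will often default to EEG even if ECoG is better, and failure to show superiority must not be read as equivalence. The stated power for 8.6 and 12.9 points would then describe added value only.
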